3.2 DISCUSSION OF TRIAL DESIGN, INCLUDING THE CHOICE OF CONTROL GROUP(S)

A parallel group design is the appropriate design as the inherent within-patient variability and the progressive nature of the disease makes it difficult if not impossible to employ a crossover design.

In order to estimate the relative drug effect on cognition and function, a double-blind comparison against placebo is included in this trial.

The current standard treatment of cognitive and functional impairment in AD shows substantial treatment effects during the first three months of treatment. Therefore, a 12-week treatment period is considered to be sufficient to assess the efficacy, tolerability and safety of BI 425809.

The data collected in this double-blind, randomised, and placebo-controlled trial are standard in this indication and will provide important information in terms of efficacy and safety on the use of BI 425809 in patients with mild-to-moderate AD.

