3.3.2 Inclusion criteria

1. Diagnosis of mild-to-moderate Alzheimer's Disease Dementia according to the recommendations from the National Institute on Aging-Alzheimer's Association workgroups on diagnostic guidelines for Alzheimer's disease (see [Section 3.3.1](#)).
2. MMSE score of 15-26 at screening (Visit 1).
3. Concomitant use of AChEIs is allowed but not required. Patients who are currently taking AChEIs are eligible as long as they have been using a stable dose for at least 3 months prior to screening and no change is foreseen for the duration of the study. This dose must be consistent with the product label in the concerned country. Patients who are not currently taking AChEIs but have taken them in the past are also eligible if AChEIs were stopped at least 3 months prior to screening.
4. All patients must sign and date an Informed Consent Form consistent with ICH-GCP guidelines and local legislation prior to participation in the trial (*i.e. prior to any trial related procedures, including any pre-trial washout of medications/medication restrictions, [Section 4.2.2.1.](#)*)

All patients must be able to give informed consent personally and have capacity for such consent. An informed consent given by a legal representative alone will not be accepted.

5. Patients must have a reliable study partner (per investigator judgment, for instance a family member, partner etc., guardian (must be always the same person)) who is in close contact with the patient, available on call and who is able to contribute to the Neuropsychological Rating Scales at specific study visits as stated in the [Flow Chart](#). This person will be able to communicate in the language in which the patient is being assessed and should also serve as a backup contact for the study site. The study partner must sign a separate informed consent form which describes their contributions during the study.
6. Patients must have at least 6 years of formal education and fluency in the test language as verbally confirmed by the patient and documented by the study investigator.
7. Male or female patients at least 55 years of age. Patients older than 85 years may be included based on an acceptable general health status, (e.g. concomitant diseases, physical capability to follow the required study procedures (visits etc.)) at discretion of the investigator.

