7.3.1.2 Secondary analyses of the primary endpoint

If considered necessary and for the purpose of further model refinement MCPmod might be repeated on the primary endpoint but with an extended set of shapes including the original candidates. Additionally to that covariates may be taken into account in a sensitivity analysis.

The primary endpoint will also be analysed using a restricted maximum likelihood estimation based on MMRM for the change from baseline in ADAS-Cog₁₁ total score after 12 weeks of

treatment. The model will include fixed, categorical covariates of treatment, visit, baseline MMSE (≥ 20 , < 20) and treatment by visit interaction, as well as the continuous fixed covariates of baseline and baseline-by-visit interaction. Patient will be considered as random effect. The unstructured covariance structure will be used to model the within patient measurements.

The first model to converge will be used as the primary analysis. The Kenward-Roger approximation will be used to estimate denominator degrees of freedom. Significance tests will be based on least-squares means using a two-sided $\alpha = 0.05$ (two-sided 95% confidence intervals).). Analyses will be implemented using SAS (version 9.4) PROC MIXED. Procedures to follow if the analysis fails to converge will be described in the TSAP.

The primary treatment comparisons will be between the placebo and the different doses of BI 425809 with respect to the mean change from baseline in the ADAS-Cog₁₁ total score after 12 weeks of treatment. Adjusted mean change from baseline as well as treatment contrasts will be presented together with the 95% confidence intervals. The primary treatment comparisons will be the contrast between treatments at the endpoint visit.

Comparisons between treatment groups will be exploratory in nature and based on the numerical comparison of the respective treatment means.

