7.6 RANDOMISATION

Eligible patients will be randomly assigned to one of the 5 treatment groups, with an allocation of 1:1:1:1:1 respectively for BI 425809 2 mg once daily: BI 425809 5 mg once daily: BI 425809 10 mg once daily: BI 425809 25 mg once daily: placebo once daily.

The randomisation will be stratified by baseline MMSE (≥ 20 , < 20). The randomisation will be done in blocks to achieve balanced allocation.

The randomisation of patients to the treatment groups will be performed via an interactive response technology (IRT). BI will arrange for the randomization and the packaging and labelling of trial medication. The randomization list will be generated using a validated system, which involves a pseudo-random number generator so that the resulting treatment will be both reproducible and non-predictable. The block size will be documented in the CTR. Access to the codes will be controlled and documented.

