7.7 DETERMINATION OF SAMPLE SIZE

The sample size calculation is based on an assumed maximum effect size of BI 425809 vs. placebo of 0.35 for the primary endpoint, as well as on the pre-specified model parameters listed in [Section 7.3.1.1](#). The assumed standardized effect size of 0.35 is based on the expectation that BI 425809 has somewhat better efficacy than AChEIs, for which results are summarized in Table 7.7:1.

Table 7.7: 1 Effect sizes for Acetyl Cholinesterase Inhibitors (AChEI)

K Rockwood (2004) [R15-5201]		AChEI Effect size (ES): Median (range)
Donepezil	}	Low Dose ES = 0.15 (0.03-0.22)
Galantamine		Medium Dose ES = 0.23 (0.12-0.29)
Rivastigmine		High Dose ES = 0.28 (0.01-0.31)

For the PoC analysis of the four BI 425809 dose groups vs. placebo using the MCPmod approach with the parameters as listed in [Section 7.3.1](#), a sample size of 95 evaluable patients per group is needed to establish PoC with 80% average power (one-sided 5% alpha level). An additional 10% of Japanese patients will be added, bringing the total to 105 evaluable patients. The primary analysis will be conducted on all patients, while an internal decision making analysis will be conducted excluding the Japanese patients.

Assuming that 10% of the randomised patients withdraw early without providing useful information, then 117 randomised patients per group are required. With 5 treatment groups, a total of 585 patients are required. [Table 7.7: 2](#) below gives the sample size calculations under different standardized effect sizes using 1-sided type I error rate of 0.05 and 80% power. The calculations for the PoC step have been performed using Dose Finding in the R-package [[R15-2001](#)] released on 28 SEP 2014 (depends on R version $\geq 2.15.0$). The R codes for the sample size calculations as well as the analyses using the MCPmod approach will be provided in the TSAP.

Table 7.7: 2 Sample size calculation under different standardized effect sizes for the ADAS-Cog₁₁ total score change from baseline with 80% power and one-sided alpha of 0.05

Standardized Effect size	0.3	0.325	0.35	0.375	0.4
Power = 80%					
N for each active treatment arm	126	107	95	81	71
N including 10% Japanese patients ¹	139	119	105	90	78
Total	695	595	525	450	390
Adjusting for 10% dropout					
N for each treatment arm ²	154	132	117	100	87
Total	772	660	585	500	433

¹ Power = 85%

² Power = 88%

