7.4.1 Primary analysis of the primary endpoint

The hypothesis testing and primary analysis are described in Sections 7.2 and 7.3.1 of the CTP, respectively.

The Multiple Comparison Procedures and Modeling (MCPMod) approach (R10-1424, R15-4293) is implemented in two main steps: (1) trial design stage; (2) trial analysis stage. The procedures for the trial design stage, including the selection of candidate models covering a suitable range of dose-response shapes and sample size and power calculations, are provided in the CTP Sections 7.3.1 and 7.7. The procedures for the trial analysis stage are specified below.

Proprietary confidential information © 2019 Boehringer Ingelheim International GmbH or one or more of its affiliated companies

The change from baseline in ADAS-Cog₁₁ at week 12 for each dose group as well as the corresponding variance-covariance matrix are estimated by an mixed effects model repeated measure including the fixed, categorical covariates of treatment, visit, baseline MMSE strata indicator (>=20, <20) and treatment-by-visit interaction, as well as the continuous fixed covariates of baseline ADAS-Cog₁₁ value and baseline-by-visit interaction. Patient is considered as random effect. The unstructured covariance matrix is used to estimate the within subject variability. The Kenward-Roger approximation will be used to estimate the denominator degrees of freedom. Analyses will be implemented using SAS 9.4 PROC MIXED. If the MMRM fails to converge, the compound symmetry covariance matrix may be considered.

The adjusted mean estimates of the doses and their estimated variance-covariance matrix from MMRM are used in the trial analysis stage. Then the multiple comparison procedure will be implemented using optimal contrast tests which control the family-wise type I error rate at one-sided $\alpha = 0.05$. The optimal contrasts corresponding to the candidate models are calculated as in the trial design stage and shown in Table 7.4.1: 1 below. They will be updated using the expected model means from candidate set and the estimated variance-covariance matrix from the data.

Table 7.4.1: 1 Optimal contrast coefficients

	Contrast coefficients for dose					
Model	Placebo	2mg	5mg	10mg	25mg	
Linear	0.419	0.320	0.170	-0.080	-0.829	
Linear Logistic	0.772	0.147	-0.094	-0.284	-0.541	
Emax	0.641	0.303	-0.009	-0.297	-0.639	
Sigmoid Emax	0.450	0.430	0.169	-0.394	-0.655	
Logistic	0.372	0.352	0.269	-0.203	-0.790	
Beta Model	0.656	-0.133	-0.392	-0.507	0.375	

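### Baseline AChEI use is collected and may be prognostic for 12-week ADAS-Cog11 change, but it is left out of the primary MMRM and the ANCOVAs: a possible small loss of precision, cheap to avoid

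*SAP*

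**What the plan says.** **Entry.** Protocol 3.3.2, criterion 3: "Concomitant use of AChEIs is allowed but not required". Current users need a stable dose for at least 3 months before screening, with no change foreseen. Past users must have stopped at least 3 months before screening.

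**Randomisation.** Protocol 7.6: "The randomisation will be stratified by baseline MMSE" (20 or more, below 20). No other stratification factor is named.

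**Primary model.** SAP 7.4.1 describes the MMRM as "including the fixed, categorical covariates of treatment, visit, baseline MMSE strata indicator" and treatment-by-visit, with baseline ADAS-Cog11 and baseline-by-visit as continuous terms. Protocol 7.3.1.2 gives the same model, and Protocol 7.3.1.1 says that it is the one fitted for MCPMod.

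**Other models.** SAP 7.4.2 reuses the MMRM. The ANCOVAs in SAP 7.4.3 and 7.5.2 contain baseline value, MMSE stratum and treatment.

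**Where AChEI use does appear.** SAP 7.2 tabulates AD-related medication at baseline. SAP Table 6.2: 1 (A1.4) makes failure of the AChEI entry criterion an important deviation with exclusion from the per-protocol set. Protocol 7.3.1.2 adds: "Additionally to that covariates may be taken into account in a sensitivity analysis". It names no covariate, and the visible SAP text does not take the option up.

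**The concern.** The sponsor treats AChEI exposure as relevant to efficacy. Protocol 1.1 and 2.1 describe these drugs as the reference treatment for mild-to-moderate disease. Protocol 7.7 uses their effect sizes as the benchmark for the trial's own assumption. A breach of the AChEI entry rule removes a patient from the per-protocol set. Yet legitimate variation in AChEI use within the rule plays no part in the visible efficacy models.

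The baseline score may not carry all the information. Protocol 1.1 says that the rate of decline depends on disease stage. A treated and an untreated patient with the same ADAS-Cog11 score could be at different underlying stages, and so have different expected 12-week changes. That is inference, and the documents give no figure for it.

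If it is so, a known baseline factor leaves explainable variance in the residual, and the dose-placebo contrasts are slightly less precise than they could be. What is at stake is efficiency, not validity.

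**Working it through.** **Inputs from the documents**
- Protocol 7.7: "assumed maximum effect size of BI 425809 vs. placebo of 0.35 for the primary endpoint"; one-sided alpha 0.05; 80% average power; 95 evaluable per group, 105 with the Japanese patients, 117 after 10% dropout.
- Protocol 7.6: five arms "with an allocation of 1:1:1:1:1 respectively".
- Protocol 7.3.1.1: the six candidate shapes. SAP Table 7.4.1: 1: the contrast coefficients.
- Protocol Table 7.7: 1: median AChEI effect sizes 0.15, 0.23 and 0.28 for low, medium and high dose.

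**Assumptions, not in the documents**
- p, the proportion of AChEI users at baseline: 0.3 to 0.8.
- g, the user versus non-user difference in 12-week change, in SD units, after baseline adjustment: 0.10 to 0.28. The upper end borrows the high-dose median for drug versus control, which is generous for stable background use.

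**Step 1: reproduce the plan's figures.** The check was a maximum test over the six optimal contrasts, by simulation (400,000 multivariate normal draws), with power averaged over the six shapes. The shapes were linear; log(dose + 0.25) for the model called linear logistic; Emax with ED50 = 8; sigmoid Emax with ED50 = 7.07 and slope 3.17; logistic with ED50 = 10 and delta = 2.28; and beta with scale 26, maximum at 10 mg and 75% at 2 mg.
- Average power is 81.4% at 95 per group (stated 80%), 84.9% at 105 (stated 85%) and 88.2% at 117 (stated 88%).
- 105/0.9 = 116.7, rounded up to 117; 5 × 117 = 585.
- Five of the six contrast rows match the SAP to three decimals. The beta row differs (placebo coefficient 0.717 against 0.656) because it depends on how its guesses are combined. With the SAP's row, power at 95 is 81.2%.

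The sample size stands.

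**Step 2: gain from the covariate.** A binary factor explains R² = p(1 − p)g² of the residual variance. Power was recomputed with the variance multiplied by 1 − R². The equivalent N is 95 × (1 − R²).

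| p | g | R² | Power, 95 per arm | Power, 105 per arm | Equivalent N |
|---|---|---|---|---|---|
| no term | – | 0 | 81.4% | 84.9% | 95 |
| 0.8 | 0.10 | 0.0016 | 81.5% | 84.9% | 94.8 |
| 0.5 | 0.23 | 0.0132 | 81.9% | 85.3% | 93.7 |
| 0.3 | 0.28 | 0.0165 | 82.0% | 85.4% | 93.4 |
| 0.5 | 0.28 | 0.0196 | 82.1% | 85.5% | 93.1 |

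The top of the range gains 0.6 to 0.7 percentage points of power, or about two patients per arm. The standard error shrinks by 1% (√(1 − 0.0196) = 0.990).

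**Step 3: chance imbalance.** At 105 per arm, the SD of the difference in user proportion between two arms is √(2p(1 − p)/105). This is 0.055 at p = 0.8 and 0.069 at p = 0.5. The 95% range of the resulting shift is 1.96 × that SD × g, from 0.011 SD (p = 0.8, g = 0.10) to 0.038 SD (p = 0.5, g = 0.28). The larger value is 11% of 0.35 (0.038/0.35). The standard error of a dose-placebo difference is √(2/105) = 0.138 SD.

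This is not a second harm on top of Step 2. At p = 0.5 and g = 0.28 the SD of the shift is 0.069 × 0.28 = 0.0193, and (0.0193/0.138)² = 0.0196, which is R² again. The imbalance is the same variance component, already inside the standard error.

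**Step 4: type I error with AChEI omitted.** With p = 0.5, g = 0.28, 105 per arm, the SAP's contrasts and 100,000 simulated trials, the rejection rate under the null is 0.051 (simulation error 0.0007), nominal for practical purposes.

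**The case against.** The strongest objection is that AChEI use may not be prognostic at all for this endpoint. The endpoint is change over 12 weeks in patients whose AChEI status has been settled for at least 3 months. Protocol 3.2 says "The current standard treatment of cognitive and functional impairment in AD shows substantial treatment effects during the first three months of treatment", so by the protocol's own account much of any AChEI effect should already sit in baseline ADAS-Cog11, which the MMRM adjusts for with a by-visit term. The effect sizes in Protocol 7.7 compare drug with control; they do not describe stable background use. This stands. A reader might infer that AChEI use acts on the primary endpoint, but no passage shows that it predicts 12-week change once baseline is adjusted for.

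A second objection is that adjusting for the stratification factor and the baseline score is a defensible pre-specified model, and that a further term of unknown value is a matter of preference. The benefit is indeed small. Doubling down on the assumption does not change that: g = 0.4 is above every value in Protocol Table 7.7: 1 (maximum 0.31), and still gives only 0.25 × 0.16 = 4% of variance, a 2% smaller standard error. But the factor is recorded and costs almost nothing to use. Protocol 7.3.1.2 already contemplates covariates without naming any, so naming this one in advance is better than leaving the choice open.

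A third objection is that the change is more than a SAP edit, because the protocol fixes the model. That is correct and is counted in the cost.

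**Conclusion.** A minor point of efficiency. Baseline AChEI use is available and may carry some prognostic information, but it is absent from the primary MMRM and the ANCOVAs. Under the stated assumptions (30-80% users, 0.10-0.28 SD residual difference), including it would remove about 0.2-2% of residual variance and add under 1 percentage point of average power. If AChEI use is not prognostic, the gain is zero.

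Three stronger readings are tempting, and the documents support none of them.
- *Imbalance in AChEI use biases the dose contrasts.* Under randomisation it is random error, only the part not explained by baseline ADAS-Cog11 and MMSE stratum remains, and the standard error already covers it. Type I error is kept.
- *The sample size is wrong.* The plan's figures reproduce.
- *The plan has no analysis by AChEI use, so a difference in drug effect between users and non-users would go unseen.* SAP 7.4.3 is headed as including a subgroup analysis whose text is not visible, so absence cannot be claimed. A main-effect covariate would not answer that question in any case.

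**What to change.** Before unblinding:
- SAP 7.4.1: add baseline AChEI use (yes/no, current use at baseline) and AChEI-by-visit as fixed effects in the MMRM that feeds MCPMod. SAP 7.4.2 then follows, since it uses the same model.
- SAP 7.4.3 and 7.5.2: add the AChEI main effect to the ANCOVAs.
- SAP Section 4: record this as a change from the model in Protocol 7.3.1.2.

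The yes/no coding puts past users with never-users, so the definition should be written down. The cost is about two degrees of freedom, a few lines of SAP text and a documented departure from the protocol's model. It needs no extra patients, visits or data.

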7.4.2 Secondary Analysis

The secondary analysis of the primary endpoint will be done by fitting the same MMRM model that is used in the MCPMod analysis in Section 7.4.1.

The primary treatment comparisons will be between the placebo and the different doses of BI 425809 with respect to the mean change from baseline in the ADAS-Cog₁₁ total score after 12 weeks of treatment. Adjusted mean change from baseline as well as the treatment contrasts will be presented together with the 95% confidence intervals. The primary treatment comparisons will be the contrast between treatments at week 12.

Comparisons between placebo and different BI 425809 doses are exploratory in nature and based on the numerical comparison of the respective treatment means.

Figures that display the adjusted means from the MMRM approach on change from baseline in the ADAS-Cog₁₁ total score for each dose level on each visit will also be presented.

7.4.3 Sensitivity analyses and subgroup analysis of the primary endpoint

The following sensitivity analyses will be done for the primary endpoint on FAS:

ANCOVA:

Analysis of covariance based on observed cases (OC) and LOCF will be used as sensitivity analyses for the primary endpoint, the model includes baseline value for the primary endpoint measure, MMSE stratification (>=20, <20) at baseline and treatment.

7.5 SECONDARY ENDPOINTS

The analyses for the secondary endpoints are described in Section 7.3.2 of the CTP.

7.5.1 Key secondary endpoints

This section is not applicable as no key secondary endpoint has been specified in the protocol.

Proprietary confidential information © 2019 Boehringer Ingelheim International GmbH or one or more of its affiliated companies

7.5.2 Secondary endpoints

The analyses of secondary endpoints are based on FAS. ANCOVA based on (OC) and BOCF will be used for the primary and sensitivity analyses of the secondary endpoints, respectively. The model will include the same corresponding variables as the ANCOVA model for the sensitivity analysis of the primary endpoint, i.e., baseline value for the corresponding secondary endpoints measures, MMSE stratification factor (>=20, <20) at baseline and treatment. For CIBIC+, CIBIS will be included as the baseline adjustment term. Comparisons between treatment groups will be considered exploratory in nature and based on the numerical comparison of the respective treatment means.

7.7 EXTENT OF EXPOSURE

Extent of exposure will be calculated as the difference between last intake of study drug and the first administration of the study drug plus one day. Descriptive statistics will be provided for number of days of exposure for each treatment arm. In addition, cumulative exposure of number and percentage (N, %) of subjects will also be displayed as "1 to < 2 weeks", "2 to <3 weeks", "3 to <4 weeks", "4 to <8 weeks", "8 to <12 weeks", ">=12 weeks" or "missing".

7.8 SAFETY ANALYSIS

All safety analyses will be performed on the treated set.

AEs will be coded based on the most current version of MedDRA®.

Analysis will be performed as defined in Section 7.3.4 of the CTP.

7.8.1 Adverse events

Unless otherwise specified, the analyses of adverse events will be descriptive in nature. All analyses of AEs will be based on the number of patients with AEs and NOT on the number of AEs.

For analysis of AE attributes such as duration, severity, etc. multiple AE occurrence data on the CRF will be collapsed into one AE event provided that all of the following applies:

- All AE attributes are identical (LLT, intensity, action taken, therapy required, seriousness, reason for seriousness, relationship and outcome)
- The occurrences were time-overlapping or time-adjacent (time-adjacency of 2 occurrences is given if the second occurrence started on the same day or on the day after the end of the first occurrence)

The analysis of adverse events will be based on the concept of treatment emergent adverse events. That means that all adverse events occurring between the date of the first drug intake till the date of the last drug intake + residual effect period will be assigned to the on-treatment period. All adverse events occurring before first drug intake will be assigned to 'screening' and all adverse events occurring after the residual effect period but within 28 days afterwards will be assigned to 'follow-up' (for listings only). For details on the treatment definition, see Section 6.1.

Adverse events of special interest (AESIs)

A hepatic injury is defined by the following alterations of hepatic laboratory parameters:

- an elevation of AST and / or ALT \geq 3 fold ULN combined with an elevation of total bilirubin \geq 2 fold ULN measured in the same blood draw sample; and / or
- marked peak aminotransferase (ALT and / or AST) elevations ≥ 10 fold ULN.

Refer to CTP Section 5.3.6.1 for details.

Analysis of other significant AEs

According to ICH E3 (12), AEs classified as 'other significant' needs to be reported and will include those non-serious and non-significant adverse events with

- (i) 'action taken = discontinuation' or 'action taken = reduced', or
- (ii) Marked haematological and other lab abnormalities or lead to significant concomitant therapy as identified by the Clinical Monitor/Investigator at a Medical Quality Review Meeting (MQRM).

AE summaries

An overall summary of adverse events will be presented. The frequency of patients with adverse events will be summarized by treatment, primary system organ class and preferred term according to MedDRA. Separate tables will be provided for patients with:

- AEs occurring with incidence in preferred term greater than 2%
- AEs occurring with incidence in preferred term greater than 5%
- AEs leading to discontinuation
- AEs leading to death
- AESIs
- Drug-related AEs
- Serious adverse events
- Series related AEs
- Other significant adverse events according to ICH E3 (12)
- Post-treatment AEs

The system organ classes will be sorted by default alphabetically, preferred terms will be sorted by frequency (within system organ class).

